2.5.2 Statistical hypothesis, model, and method of analysis

The primary null hypotheses are:

- $H_{0\ 450}$: the reduction in the polyp size at 16 weeks from the baseline as measured by the NPS in fevipiprant 450 mg QD plus the SoC is less than or equal to the reduction in the polyp size as measured by the NPS in placebo plus the SoC for the population.
- $H_{0\ 150}$: the reduction in the polyp size at 16 weeks from the baseline as measured by the NPS in fevipiprant 150 mg QD plus the SoC is less than or equal to the reduction in the polyp size as measured by the NPS in placebo plus the SoC for the population.

[figure not shown]
The primary alternative hypotheses are:

- $H_{A\ 450}$: the reduction in the polyp size at 16 weeks from the baseline as measured by the NPS in fevipiprant 450 mg QD plus the SoC is greater than the reduction of the polyp size as measured by the NPS in placebo plus the SoC for the population
- $H_{A\ 150}$: the reduction in the polyp size at 16 weeks from the baseline as measured by the NPS in fevipiprant 150 mg QD plus the SoC is greater than the reduction of the polyp size as measured by the NPS in placebo plus the SoC for the population

Familywise Type I error rate control

The familywise type I error rate will be controlled at a 1-sided 2.5% level across the primary null hypothesis using graphical approach specified by Figure 2-1 (Bretz et al 2011). The Dunnett test will be used to test $H_{0\ 450}$ and $H_{0\ 150}$

Figure 2-1 Representation of Approach to Test Hypothesis

Vertices with associated weights denote the individual null hypotheses and their local significance levels (initially the alpha is split 50%:50% across the primary null hypotheses regarding the two dose levels). Directed edges between the vertices specify how the local significance levels are propagated in case of significant results.

Statistical model for primary variable

The primary efficacy endpoint is mean change in nasal polyp score from baseline to Week 16. Baseline NPS is defined as the last measurement performed on or before the date of randomization. The absolute change from baseline NPS values will be defined as the NPS at the timepoint minus the NPS at baseline.

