The primary efficacy variable will be analyzed using a mixed model repeated measures (MMRM) approach (fevipiprant 450 mg plus SoC and fevipiprant 150 mg plus SoC). The model will include change from baseline to follow-up timepoints every 8 weeks through week 16 as response variables, fixed-effects factors for treatment, visit, treatment \times visit interaction, nasal

polyp score baseline value, and baseline \times visit interaction. An unstructured correlation structure will be assumed for the repeated measures within patients. Parameters will be estimated using the restricted maximum likelihood method with the Newton- Raphson algorithm. The least square mean change in nasal polyp score from baseline to week 16 alongside with 95% confidence interval and the P-value corresponding to the least square mean difference will be presented. The change in the least square mean will also be plotted by visit.

The change from baseline in NPS will be summarized by treatment arm and timepoint

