5.4 Statistical models

5.4.1 Primary analysis

The primary endpoint for this study is the efficacy in terms of change from baseline in the nasal polyp score of fevipiprant 450 mg plus SoC and fevipiprant 150 mg plus SoC over placebo plus SoC.

The following mixed model with repeated measures will be used for changes from baseline in the Nasal Polyp Score :

Change from baseline = intercept + treatment + visit + treatment * visit + NPS baseline value + NPS baseline value * visit + error

The random effect in the mixed model will be represented by the use of an unstructured covariance matrix for the within patient variability.

The SAS procedure MIXED will be used with the following code :

```
proc mixed data=...order=internal;
  **include schedule assessments/visits only;
  where avisitn in (201,208,216);
  class trt avisitn;
  model chg= trt avisitn trt*avisitn base base*avisitn /ddfm=kr;
  repeated avisitn/subject=usubjid type=un;
  lsmeans trt*avisitn/ cl diff;
```

```
adjust=DUNNET;
```

```
run;
```

where chg = change from baseline

trt = treatment (QAW 450 mg + SoC , QAW 150 mg +SoC , Placebo+SoC)

avisitn = visit (include scheduled visit and assesments only)

base = baseline Nasal Polyp Score

usbjid = unique subject identifier

Appropriate baseline values and visits will be included for each of the endpoints i.e. Nasal Congestion Score, SNOT-22 score and the UPSIT smell test score.

The default estimation method for the covariance parameters will be used, which is the restricted maximum likelihood.

Results will be presented with least square means and standard errors (SE) for treatment effects and least square mean, SE, associated two sided 95% confidence interval , a two sided p-value for treatment contrast QAW-Placebo at each visit.

If the analysis fails to converge with an unstructured covariance matrix, either a compound symmetry (first choice) or the first order auto regressive (AR1) (second choice) covariance structure will be used.

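### The primary-analysis code printed in SAP 5.4.1 does not carry out the two-comparison week-16 Dunnett test that SAP 2.5.2 specifies

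*SAP*

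**What the plan says.** SAP 2.5.2 sets two one-sided null hypotheses at week 16, one per dose against placebo. On error control it states: "The familywise type I error rate will be controlled at a 1-sided 2.5% level". It names the test ("The Dunnett test will be used to test" the two hypotheses) and places it in a graphical procedure. Alpha is first split equally between the doses and is passed on after a rejection. The model uses "follow-up timepoints every 8 weeks through week 16 as response variables", that is, weeks 8 and 16.

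SAP 5.4.1 then commits to an implementation: "The SAS procedure MIXED will be used with the following code". Four parts of that section matter here:

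- The visit filter is "where avisitn in (201,208,216", three codes, none of them defined.
- The comparison line is "lsmeans trt*avisitn/ cl diff", followed by a semicolon.
- The adjustment, "adjust=DUNNET", stands after that semicolon as a line of its own.
- The results text promises two-sided 95% intervals and "a two sided p-value for treatment contrast QAW-Placebo at each visit". It does not say whether they are adjusted or which of them decides the primary test.

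SAP 2.6 defines no key secondary endpoints, so this is the trial's only confirmatory test.

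**The concern.** The SAP gives both a verbal specification and a program for the primary test, and the two do not agree. Someone who follows the code as printed does not obtain the test in SAP 2.5.2. Someone who repairs it has to choose the comparison family, the control, the time point and the deciding p-value, and SAP 5.4.1 settles none of these.

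The plausible outcomes err in opposite directions. Unadjusted p-values are too lenient. A Dunnett adjustment spread over treatment-by-visit cells is too strict. Either can change the verdict on a dose, so the choice should not be left until the treatment codes are available.

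**Working it through.** **Reading the code against SAP 2.5.2**

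| Element | SAP 2.5.2 | Code in SAP 5.4.1 |
|---|---|---|
| Comparisons | 2 (each dose against placebo) | all differences among treatment-by-visit cells |
| Control | placebo | none named |
| Time point | week 16 | all visits kept |
| Adjustment | Dunnett with propagation | outside the LSMEANS statement |
| Visits | 8-weekly to week 16 (2) | 201, 208, 216 (3 codes) |

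A semicolon ends a SAS statement, so the Dunnett option is not part of LSMEANS as printed. The code was not run in SAS for this review.

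**Inputs.** SAP 3 gives effect 1.5, SD 1.8, one-sided alpha 0.0125 per comparison, power 80%, dropout 10% and 31 per arm.

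**Reproducing the plan's figures.** Per arm, n = 2 × [1.8 × (2.2414 + 0.8416) / 1.5]² = 27.37, which rounds up to 28. Then 27.37 / 0.9 = 30.4, which rounds up to 31 per arm, or 93 in total. With 28 per arm, a large-sample Dunnett test has 92.4% power to reject for at least one dose when both effects are 1.5; the SAP says about 93%.

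**Set-up for the scenarios.** 28 completers per arm (31 × 0.9 = 27.9), df = 3 × 28 − 3 = 81, SE = 1.8 × √(2/28) = 0.4811, noncentrality = 1.5 / 0.4811 = 3.118. This uses week-16 data with a pooled variance and ignores any gain from the repeated-measures model.

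**Specified test, two comparisons, correlation 0.5**

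- The one-sided 2.5% Dunnett critical t is 2.251, so the cut-off for a first rejection is 2.251 × 0.4811 = 1.08 NPS points.
- This corresponds to an unadjusted two-sided p of 0.0271.
- Single-step power is 80.5% per dose.
- If all alpha passes on after a rejection (an assumption, since the figure is not shown), the second dose is tested at t = 1.990. With both effects at 1.5, power per dose is then about 84.7%.

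**Scenario 1: unadjusted differences read at two-sided 0.05**

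- The critical t is 1.990 and the cut-off is 1.990 × 0.4811 = 0.96 points.
- The chance of at least one false positive in the favourable direction is 4.5%, against the specified 2.5%.
- A benefit between 0.96 and 1.08 points would be declared significant even when the other dose is not rejected. In that case the SAP 2.5.2 test would not reject.

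**Scenario 2: semicolon moved, Dunnett over cells against the week-16 placebo cell**

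- Two visits give 3 × 2 = 6 cells, so 5 comparisons. Three visits give 3 × 3 = 9 cells, so 8 comparisons.
- The documents give no between-visit correlation, so 0.3 to 0.7 is assumed, with equal variances. Critical values are simulated.

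| Family | Critical t | Power per dose |
|---|---|---|
| 2 (specified, single-step) | 2.25 | 80.5% |
| 5 | 2.53-2.56 | 71-72% |
| 8 | 2.67-2.71 | 66-67% |

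The 5-comparison family includes cross-visit pairs, such as placebo at week 8 against placebo at week 16, that are no part of the hypotheses. If the control were any other cell, the two week-16 dose-minus-placebo contrasts would not both be in the family. The 8-comparison row treats 201 as an ordinary visit.

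**The case against.** The best defence is that SAP 2.5.2 governs. It fixes the hypotheses, week 16, the Dunnett test and the error level, and nothing in the SAP says that an unadjusted p-value decides. The code names Dunnett, so the intention is plain. It is a skeleton with an elided dataset name, and a stand-alone adjustment line is more likely to be noticed as an error than to give a silent unadjusted result. That is fair as to intent. But SAP 5.4.1 says this code will be used, and correcting the semicolon still leaves the family, control and time point wrong or open.

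Five stronger readings are tempting, and the documents do not support them:

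- *The trial's type I error is 4.5%.* That figure applies only if unadjusted p-values are used for the decision, which SAP 2.5.2 excludes.
- *Any benefit between 0.96 and 1.08 points would be wrongly declared.* SAP 2.5.2 propagates alpha. Under full propagation with both effects at 1.5, about 66% of results in that window are rejected legitimately because the other dose has already been rejected.
- *Two-sided p-values contradict a one-sided test.* A two-sided 5% Dunnett test, read in the favourable direction, has the same critical value. What is missing is a label and a decision rule, which is mainly a presentation gap.
- *Dunnett would run over four contrasts, two doses at two visits, each against placebo at the same visit.* The printed LSMEANS request would not give that family, and SAP 2.5.2 confines the test to week 16.
- *Visit 201 damages the model.* The code is undefined. If it is Day 1, SAP 2.1.3.7 and 2.1.3.8 suggest that a pre-dose record has no change value to model. It is an inconsistency with no demonstrated effect.

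**Conclusion.** The code in SAP 5.4.1 is wrong as written and should be corrected. It leaves the adjustment outside LSMEANS, and attaching it there would still not give the two week-16 comparisons. The sizes above (4.5% familywise error if unadjusted p-values decide; power per dose of 71-72% or 66-67% if Dunnett spans the cells) describe what could follow from the code, not what the SAP intends. They rest on 28 completers per arm, SD 1.8, effect 1.5, df 81 and, for the power losses, an assumed between-visit correlation of 0.3 to 0.7. The hypotheses, the alpha level and the sample size of 93 stand. The point is worth fixing because it concerns the only confirmatory test and the correction is small.

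**What to change.** In SAP 5.4.1:

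1. Define the visit codes and restrict the NPS model to weeks 8 and 16 (208 and 216, if those are their codes).
2. Replace the LSMEANS and adjustment lines with two explicit week-16 contrasts: 450 mg minus placebo and 150 mg minus placebo.
3. Apply the Dunnett adjustment to those two contrasts only, with the propagation shown in Figure 2-1, and say that this is a step-down procedure.
4. State that a null hypothesis is rejected when its adjusted one-sided p-value is at most 0.025.
5. Label unadjusted p-values and intervals, and results at other visits, as descriptive.

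The cost is a few lines of SAP code and text, to be settled before unblinding. The protocol, sample size and data collection do not change.

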5.4.2 Key secondary analysis

There are no key secondary endpoints for this study.

5.5 Rule of exclusion criteria of analysis sets

The following protocol deviations will lead to exclusion of patients from FAS, SCR or safety set :

PD Identifier	'PD Description' for reporting	CP_Exclude from analysis sets
INCL01A	Did not sign informed consent	Exclude from all analysis sets
INCL01B	Written informed consent obtained after date of a study assessment	All concerned assessments removed from SCR
TRT01	Received study drug but not randomized	Exclude from FAS and SAF (also evaluate on a case by case basis)
TRT02	Randomized but no study drug given	Patient did not recieve a study drug; then exclude

		from FAS and SAF; otherwise do not exclude from any population set
EXCL19	History of sinus or nasal surgery modifying the structure of the nose such that assessment of NPS via nasal endoscopy is not possible.	Exclude from all analysis sets
INCL02B	No current diagnosis of nasal polyposis	Exclude from all analysis sets
INCL02C	Diagnosis of nasal polyposis with polyp size score is less than 4 and a less than 2 score in each nostril, measured by nasal endoscopy at SCR and prior to randomization on Treatment Day 1.	Exclude from Full analysis set.

6 Reference

Bachert et al .(2016) Effect of Subcutaneous Dupilumab on Nasal Poly Burden in Patients With Chronic Sinusitis and Nasal Polyposis. A Randomized Clinical Trial . Journal of the American Medical Association ; Volume 315, Number 5 : 469-479

Bretz F, Tamhane A , Dmitrienko A , Multiple Testing Problems in Pharmaceutical Statistics (2010) : CRC Press

Gaveart et al (2011) Mepolizumab, a humanized anti- IL-5 mAb, as a treatment option for severe nasal polyposis . Journal of Allergy and Clinical Immunology ; Volume 128 , Number 5 : 989-995

Niloofer Ramezani , Analyzing Corelated Data in SAS[®] , Paper 1251-2017 , SAS Institute Inc.

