### **12.1 Analysis sets**

[figure not shown]
The Full Analysis Set (FAS) will be comprised of all randomized patients who meet both of the following criteria:

- Received at least one dose of study treatment
- Have a baseline NPS score  $\geq 4$  as measured by the central reader.

According to the intent to treat principle, subjects will be analyzed according to the treatment they have been assigned to at the randomization. However, if patients received study treatment without being randomized into the study they will be excluded from the FAS.

The Safety Analysis Set (SAF) includes all subjects who received at least one dose of study treatment. Subjects will be analyzed according to the study treatment received, where treatment received is defined as the randomized/assigned treatment if the patient took at least one dose of that treatment or the first treatment received if the randomized/assigned treatment was never received.

The analysis of the primary objectives will be performed on the FAS. The FAS will be used for the analysis of all other efficacy variables. The SAF will be used in the analysis of all safety variables.

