The statistical analysis plan (SAP) describes all planned analyses for the Clinical Study Report (CSR) of study QAW039A2322, a phase IIIB, 16 week multicenter, randomized, double-blind, parallel-group, placebo-controlled study of fevipiprant once daily plus standard-of-care (SoC) for assessment of the efficacy in reduction of nasal polyp size in patients with nasal polyposis and concomitant asthma

The content of this SAP is based on the protocol of QAW039A2322 version v03.

The purpose of the statistical analysis plan is to describe the implementation of the statistical analysis planned in section 12 of the study protocol. Data will be analyzed by Novartis according to the data analysis section 12 of the protocol which is available in [Appendix 16.1.1 of the CSR](#). Important information is given in the following sections and the details will be provided, as applicable, in [Appendix 16.1.9 of the CSR](#).

[figure not shown]

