2.2 Analysis sets

The **Screened Set (SCR)** will consist of all patients who provided informed consent

The **Full Analysis Set (FAS)** will be comprised of all randomized patients who meet both of the following criteria:

- Received at least one dose of study treatment
- Have a baseline NPS score ≥ 4 as measured by the central reader.

According to the intent to treat principle, subjects will be analyzed according to the treatment they have been assigned to at the randomization. However, if patients received study treatment without being randomized into the study they will be excluded from the FAS.

The **Safety Set (SAF)** includes all subjects who received at least one dose of study treatment. Subjects will be analyzed according to the study treatment received, where treatment received is defined as the randomized/assigned treatment if the patient took at least one dose of that treatment or if the patient received more than one treatment, then the patient would be analyzed according to the randomized treatment.

The analysis of the primary objectives will be performed on the FAS. The FAS will be used for the analysis of all other efficacy variables. The SAF will be used in the analysis of all safety variables.

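### SAP 5.5 takes some dosed patients out of the Safety Set, and SAP 2.7.7.2 defines 'worsening' so that it adds no patient to 'newly occurring'

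*SAP*

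**What the plan says.** **Safety Set.** SAP 2.2 says the SAF "includes all subjects who received at least one dose of study treatment"; Protocol 12.1 defines it the same way. Both documents also address the patient who was dosed but never randomized, and name one consequence: "if patients received study treatment without being randomized into the study they will be excluded from the FAS".

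SAP 5.5 opens with "The following protocol deviations will lead to exclusion of patients from FAS, SCR or safety set". For EXCL19 (nasal anatomy altered by surgery so that NPS cannot be assessed) and INCL02B (no current nasal polyposis) the action is "Exclude from all analysis sets". For TRT01 (dosed, not randomized) it is "Exclude from FAS and SAF (also evaluate on a case by case basis)". SAP section 4 records no change from the protocol's analyses.

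For treatment received, Protocol 12.1 uses the randomized treatment if any of it was taken, otherwise "the first treatment received if the randomized/assigned treatment was never received". SAP 2.2 has no such fallback. Its second clause reads "if the patient received more than one treatment, then the patient would be analyzed according to the randomized treatment".

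**Notable values.** Protocol 12.5.1 promises a count of patients with newly occurring or worsening on-treatment laboratory abnormalities and does not define the two terms. SAP 2.7.7.2 defines both. *Newly occurring* needs a baseline that is not notable. *Worsening* needs a baseline that is not notable and a worse value afterwards. The value counted must itself meet the notable criteria. SAP 2.8.2 applies the same approach to vital signs. SAP 2.8.1 uses the two terms for QTcF without defining them.

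**The concern.** A safety set exists to describe everyone exposed. EXCL19 and INCL02B are eligibility failures: they may make NPS uninterpretable, but they say nothing about exposure. Removing such patients after dosing drops their adverse events, laboratory values, ECGs and vital signs from the SAF summaries and from the public disclosure tables, which SAP 2.7.5.2 runs on the safety set. For TRT01, SAF membership is left to discretion with no criterion. A programmer following 2.2 and one following 5.5 would build different sets.

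The second defect concerns a definition with no content of its own. The phrase *newly occurring or worsening* promises two groups, but the SAP's wording delivers one. The group that drops out, patients already abnormal who become more abnormal on drug, is of safety interest.

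**Working it through.** **1. Rows of SAP 5.5 against the SAF definition**

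| Row | Action in SAP 5.5 | Agrees with SAF = dosed? |
|---|---|---|
| EXCL19 | out of all sets | No |
| INCL02B | out of all sets | No |
| TRT01 | out of FAS and SAF, discretion | No; SAP 2.2 and Protocol 12.1 name the FAS only |
| INCL02C (NPS too low) | out of FAS | Yes |
| TRT02 (randomized, undosed) | out of FAS and SAF if undosed | Yes |
| INCL01B (late consent) | assessments out of SCR | Yes |
| INCL01A (no consent) | out of all sets | Has its own consent rationale; not contested |

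The table is also uneven: INCL02C, another nasal-polyp eligibility failure, is correctly confined to the FAS.

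**2. Size of removing one patient.** The documents give no expected number of such patients. Illustration: n = 31, the planned randomized number per arm, and k patients with an event, assumed to be 1, 3 or 10. Formulas: k/31 with all patients kept; k/30 if the removed patient had no event; (k − 1)/30 if the removed patient had the event.

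| k | All kept | Removed, no event | Removed, with event |
|---|---|---|---|
| 1 | 1/31 = 3.2% | 1/30 = 3.3% (+0.11 points) | 0/30 = 0.0% (−3.23) |
| 3 | 3/31 = 9.7% | 3/30 = 10.0% (+0.32) | 2/30 = 6.7% (−3.01) |
| 10 | 10/31 = 32.3% | 10/30 = 33.3% (+1.08) | 9/30 = 30.0% (−2.26) |

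**3. Logic of the two terms.** Let N be the patients with a non-notable baseline and a notable on-treatment value. *Worsening* as written is N plus the condition that the later value is worse than baseline. That is a subset of N, so the union of the two terms is N and *worsening* adds 0.

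Two grids confirm this:
- ALT (notable above 3 × ULN), eight values, four of them notable. *Newly occurring* pairs: 4 × 4 = 16. *Worsening* pairs as written: the same 16, so 0 added. Pairs rising from a notable baseline: 4 × 3/2 = 6, none counted.
- Potassium (notable below 3 or above 6 mmol/L), eight values, two notably low and two notably high. *Newly occurring*: 4 × 4 = 16; *worsening* adds 0. Uncounted pairs: 2 more extreme in the same direction, plus 2 × 2 × 2 = 8 that switch from one notable side to the other, 10 in all.

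**4. Can a notable baseline occur?** Table 5.3.2 has 4 hematology + 11 chemistry = 15 parameters. Five have two bounds (thrombocytes, WBC, potassium, glucose, sodium), so the switching problem applies to them. Numeric entry limits in Protocol 5.2:
- None on the parameter itself (9): hematocrit, hemoglobin, thrombocytes, alkaline phosphatase, potassium, glucose (HbA1c only), BUN/urea, sodium, gamma GT.
- CK: 2 × ULN for statin users only; the notable bound is 4 × ULN for everyone.
- WBC: entry limit 2500 cells/µL = 2.5 × 10⁹/L, below the notable bound of 2.8. A patient entering at 2.7 and falling to 1.5 is not counted.
- Bilirubin (1.3 × ULN) and creatinine (through eGFR): limits in units other than those of the notable bounds.
- ALT and AST: 2.0 × ULN at entry against 3 × ULN notable, the only two closed directly by number.

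Total: 9 + 1 + 1 + 2 + 2 = 15. These limits apply at Screening (days −42 to −28), whereas laboratory baseline under SAP 2.1.3.6 is the Day 1 pre-dose sample, about 4 to 6 weeks later.

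**5. Vital signs and QTcF.** SAP 2.8.2 imports the rule but does not say whether the baseline filter also governs the change criteria in Table 2.8.2, so whether larger deteriorations are still captured is open. For QTcF, exclusion 5 applies the same 450/460 msec limits at screening, so notable baselines should be rare.

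**The case against.** The strongest objection is rarity. Protocol 8.3.1 and Appendix 7 require a central reading confirming NPS before randomization, so an EXCL19 or INCL02B patient could be dosed only through a serious breach. The likelier failure, a low NPS, is handled correctly. Exclusions are listed (SAP 2.3.3), all safety data are listed (SAP 2.1.3.9), and deaths after first dose are tabulated (SAP 2.7.6). All of this stands and limits the impact. It does not reconcile two sections that give opposite instructions, and listings do not replace incidence tables.

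On TRT01, SAP 2.1.3.1 ties study treatment to assignment at randomization, so a never-randomized patient might be said to have received none. SAP 2.2 rules that reading out, because it speaks of study treatment received without randomization. Discretion could also be used to keep such a patient in, but no criterion says when. It is fair that the protocol's fallback clause was not written specifically for TRT01, so the SAP should state that it covers that case.

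On the missing clause, SAP section 1 says "Data will be analyzed by Novartis according to the data analysis section 12 of the protocol", so the protocol's rule still applies. That reduces the omission to incompleteness.

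On *worsening*, a stray negative is the likely cause, and the protocol gives no definition to contradict. But the text is what gets programmed, and a second term that can never add a patient is not what the ordinary meaning of the protocol's phrase promises. Exclusions 34 and 35 let the investigator exclude other abnormalities, and exclusion 35 names hypokalemia and uncontrolled hypertension. These are judgements without numeric limits. The vital-sign bounds are extreme (for example systolic below 75 or above 200 mmHg), so notable baselines there should be few. The QTcF section also tabulates increases that need no normal baseline, so the effect there is small.

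**Conclusion.** Both points hold. SAP 5.5 contradicts the SAF definition in SAP 2.2 and Protocol 12.1 for three rows, without declaring a change. SAP 2.7.7.2 makes *worsening* redundant for all 15 parameters.

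The impact is minor to moderate. The first point matters only if such a patient was dosed. One removal then moves an arm's incidence by +0.1 to +1.1 points, or by −2.3 to −3.2 points if that patient had the event; this assumes 31 per arm and 1, 3 or 10 patients with the event. The number affected by the second point cannot be derived from the documents. The worst-value change summary in SAP 2.7.7.1 and the listings still show the deterioration, but the notable-value count leaves it out. The primary efficacy analysis is untouched. The SAP should be corrected because, followed as written, it gives wrong safety denominators and incomplete counts.

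**What to change.** - **SAP 5.5:** confine EXCL19 and INCL02B to the FAS, as INCL02C already is. Keep every dosed, consented patient in the SAF, and delete the case-by-case note for SAF membership.
- **SAP 2.2:** restore the protocol's fallback to the first treatment actually received, and state that it also assigns TRT01 patients to a treatment group.
- **SAP 2.7.7.2:** define *worsening* as a notable baseline followed by a notable value further beyond the bound in the same direction. Count a notable value in the opposite direction as *newly occurring*. Keep the existing missing-baseline rule.
- **SAP 2.8.1 and 2.8.2:** apply the same definitions to QTcF and vital signs, and state whether the baseline filter applies to the change criteria in Table 2.8.2.

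The cost is SAP wording and the matching programming; no new data are needed. SAF counts change only if such patients were dosed. One downside: with no minimum change, small fluctuations beyond a bound can add a few *worsening* counts.
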